5.1 Dosage and Administration

Treatment will be administered on an outpatient basis.

Table 5.1 Regimen Description

Study Drug	Dose	Route	Schedule	Cycle Length
BYL719	350 mg	PO	daily	Pre-operative window (10-21 days) or up to 28 days for delayed surgery

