	
check FPG at least weekly for 8 weeks, then continue checking at least every 2 weeks, alert treating physician if FPG>250mg/dl
 
 • If FPG does not resolve to Grade1 within 3-5 days while off study treatment and on metformin, consult a diabetologist for management of diabetes is strongly recommended. If FPG does not resolve to ≤ Grade 1 within 21 days after institution of appropriate anti-diabetic treatment in cooperation with diabetologist and exclusion of confounding factors e.g. urinary tract infection, permanently discontinue patient from BYL719 treatment
Grade 4 (> 500 mg/dL) [≥ 27.8 mmol/L]	
Omit BYL719 confirm fasting status of the assessment. If non-fasting, re-check within 24 hours.
 
Exclude confounding factors like e.g. urinary tract infection.
 
Administer intravenous hydration and intervention for electrolyte/ketoacidosis/hyperosmolar disturbances as clinically appropriate.
 
Consider cooperation with diabetologist, initiate or intensify medication with appropriate anti-diabetic treatment (see Grade 3), re-check within 24 hours.
 
 • If grade improves then follow specific grade recommendations • If FPG is confirmed at Grade 4 and confounding factors could be excluded, permanently discontinue patient from BYL719

A diabetologist consultation should always be considered.
 
In case metformin is contraindicated or not tolerated even at low dose, another insulin-sensitizer (e.g., pioglitazone) may represent an alternative.
 
For all grades: instruct patient to follow dietary guidelines according to local and/or institutional standards for management of diabetes mellitus (such as those provided by the American Diabetes Association) during the study, e.g., small frequent meals, low carbohydrate content, high fiber, balancing carbohydrates over the course of the day; three small meals and 2 small snacks rather than one large meal
	

Investigations (Hematologic)
	

Neutropenia (ANC)
	
Grade 1 (ANC < LLN - $1.5 \times 10^9/L$) Grade 2 (ANC < $1.5 - 1.0 \times 10^9/L$)	Maintain dose level
Grade 3 (ANC < $1.0 - 0.5 \times 10^9/L$) Grade 4 (ANC < $0.5 \times 10^9/L$)	
Omit dose until resolved to ≤ Grade 1, then:
 
 • If resolved in ≤ 7 days, then maintain dose level

	
 ● If resolved in > 7 days, then ↓ 1 dose level
Febrile neutropenia	

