10.3 Protocol Early Stopping Rules

10.3.1 Toxicity

A continuous monitoring rule for safety will be instituted, to guard against excess toxicity from pre-operative treatment with BYL719 at 350 mg po daily, the RP2D for this agent. All patients will be treated at the dose of BYL719 350 mg po daily. After enrollment of the 6th patient, we will continuously monitor the number of patients who discontinue BYL719 and come off study for BYL719-attributable toxicity. A qualifying toxicity must be at least possibly related to BYL719, as judged by the treating investigator, and fulfill one of the following definitions:

- Grade ≥ 3 non-hematologic toxicity, with the exception of asymptomatic electrolyte abnormalities manageable with repletion.
- Intolerable non-hematologic toxicities of any grade, which persist despite optimal medical management.
- Grade ≥ 3 thrombocytopenia or neutropenia.
- Any grade toxicity that results in a significant delay of surgery, defined as more than 42 days from the start of BYL719 protocol treatment.

If the posterior probability of $\geq 33\%$ toxicity rate exceeds 50% for patients having to discontinue window treatment due to qualifying toxicity, this would be considered unacceptable. The study would be placed on hold and would be referred to the UACC DSMB for evaluation of excess toxicity and recommendations for design change or study closure.

Table 8 below describes the number of toxicity events per number of treated patients required to trigger referral to the UACC DSMC. Table 8 also shows the posterior probability that the rate exceeds 33%, and the binomial probability associated with the decision for an assumed 33% discontinuation rate. The prior probability has a beta distributions with parameters $a = 1$ and $b = 9$, assumes a 10% mean with an approximate 80% mid-range of .0 to .22.

Table 8. Boundaries for the Excess Toxicity Rule

Subjects	Treatment-Related Discontinuations	PP($\pi > 33\%$)*	Pr($X \geq r p = .33$)
6	5	.629	.017
8	6	.685	.019
11	7	.673	.037
14	8	.664	.054
17	9	.657	.071
20	10	.650	.087

* π is the discontinuation rate. The minimum acceptable upper bound of a treatment-related discontinuation is 33%. PP($\pi > 33\%$) is the posterior probability that the discontinuation rate exceeds this 33% upper bound. This posterior probability of discontinuation is calculated from the prior distribution, the number of subjects treated and the observed number of treatment-related discontinuations.

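### Section 10.3.1 does not define one counted event for Table 8, so a patient whose drug is omitted for qualifying toxicity and not resumed before surgery need not be counted

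*Combined protocol and SAP*

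**What the plan says.** Section 10.3.1 starts continuous safety monitoring after the sixth patient: "we will continuously monitor the number of patients who discontinue BYL719 and come off study for BYL719-attributable toxicity". It then lists four kinds of qualifying toxicity. The fourth is "Any grade toxicity that results in a significant delay of surgery, defined as more than 42 days from the start of BYL719 protocol treatment". The trigger is a posterior probability above 50% that the rate is 33% or more "for patients having to discontinue window treatment due to qualifying toxicity, this would be considered unacceptable". The study then goes on hold and is referred to the board.

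The event column of Table 8 is headed as treatment-related discontinuations. Its footnote says the posterior comes from the prior, "the number of subjects treated and the observed number of treatment-related discontinuations". The sentence introducing the table instead describes its entries as toxicity events relative to patients treated.

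Three other provisions bear on this:

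- Sections 5.3 and 5.6 treat interruption and discontinuation as separate actions. For Grade 3 hyperglycemia the drug is omitted, and permanent discontinuation follows if glucose has not recovered "within 21 days after institution of appropriate anti-diabetic treatment in cooperation with diabetologist and exclusion of confounding factors".
- Table 5.1 gives the treatment period as "Pre-operative window (10-21 days) or up to 28 days for delayed surgery".
- Section 10.3.2 has a separate rule. More than 3 patients among the first 14 with surgery after day 42, because of a toxicity possibly related to the drug, stops enrollment.

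**The concern.** One boundary has three descriptions of its numerator: discontinued and off study, discontinued, and toxicity events. The four listed toxicities say which reasons qualify; on the operative wording they are not counted by themselves. Two kinds of patient then have no clear place.

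1. **Omitted and not resumed.** The drug is omitted for a qualifying toxicity and surgery arrives before it is restarted. The protocol does not say whether this is an interruption or a discontinuation.
2. **Delayed after dosing.** Dosing was completed and a toxicity then pushes surgery past day 42. This patient meets the fourth item but has not discontinued anything.

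A treated patient who is not counted stays in the Table 8 denominator as a patient without an event, which pulls the posterior down. The first kind may also have fewer than 10 doses. Such a patient is not evaluable under Sections 7 and 10.2.1, so enrollment continues in their place while Table 8 may register nothing. If two members of staff can classify the same patient differently, the rule's operating characteristics are not defined.

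**Working it through.** **1. Reproduce Table 8.** Inputs from Section 10.3.1: prior Beta(1, 9), bound 0.33, trigger 0.50. After r counted patients among n, the posterior is Beta(1 + r, 9 + n − r). The last column of Table 8 is the binomial tail P(X ≥ r) at p = 0.33.

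| n | r | Posterior, Table 8 | Recomputed | Tail, Table 8 | Recomputed |
|---|---|---|---|---|---|
| 6 | 5 | .629 | .6291 | .017 | .0170 |
| 8 | 6 | .685 | .6847 | .019 | .0187 |
| 11 | 7 | .673 | .6732 | .037 | .0366 |
| 14 | 8 | .664 | .6641 | .054 | .0545 |
| 17 | 9 | .657 | .6565 | .071 | .0712 |
| 20 | 10 | .650 | .6502 | .087 | .0866 |

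All rows agree to rounding. With one event fewer, the posterior is .415 to .498, below the trigger. The full continuous boundary is 5 at n = 6–7, 6 at 8–10, 7 at 11–13, 8 at 14–16, 9 at 17–19 and 10 at 20. The arithmetic is sound for whatever is counted.

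**2. Interruption against the window.** Planned surgery falls on days 11–22, at the latest day 29 (Section 6.3.1). If anti-diabetic treatment starts on day d, the 21-day limit for Grade 3 hyperglycemia falls on day d + 21. The first scheduled on-treatment glucose check is day 8 ± 3 (Section 6.2.3):

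- d = 5 gives day 26, after the planned surgery days.
- d = 8 gives day 29, the last permitted surgery day.

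This route will therefore usually not end in discontinuation before surgery. For Grade 3 neutropenia, thrombocytopenia, diarrhea, rash and other adverse events, the Section 5.6 table omits the drug until recovery and sets no time at which omission becomes discontinuation.

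**3. Delay against dosing.** Dosing ends by day 28 (Table 5.1). The fourth item needs surgery after day 42, which is at least 42 − 28 = 14 days later. A patient who completed dosing cannot register as a discontinuation.

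**4. One worked case.** At n = 14, take 5 discontinuations plus 3 patients whose drug was omitted and not resumed.

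- Counting 5: Beta(6, 18), posterior .178, no hold.
- Counting 8: Beta(9, 15), posterior .664, hold.

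**5. Chance of a hold by patient 20.** Counted rate = true rate × captured share. The true rate here is that of qualifying toxicity ending treatment, whether by discontinuation or by omission without resumption. Neither quantity is in the documents, so both are assumptions. The probability of ever reaching the step 1 boundary was computed exactly, patient by patient from n = 6 to 20.

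| True rate | 100% captured | 75% | 50% |
|---|---|---|---|
| 33% | 19.2% | 5.0% | 0.6% |
| 40% | 40.0% | 12.6% | 1.6% |
| 50% | 72.5% | 31.9% | 5.3% |
| 60% | 92.9% | 56.9% | 12.6% |

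If the rule is applied only at the six sample sizes printed in Table 8, the figures are 12.0%, 2.4% and 0.2% at a true 33%, and 63.4%, 22.3% and 2.6% at 50%.

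**6. The separate delay rule.** Section 10.3.2 acts at 4 or more of the first 14. The chance of reaching that is 4.4% at a true delay rate of 10%, 30.2% at 20% and 73.0% at 33%. Its boundary of 4 of 14 is half the Table 8 boundary of 8 of 14.

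**The case against.** Several stronger readings are tempting, and the documents do not support them.

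- **That omitted patients are never counted.** Section 10.3.1 does not require discontinuation to be permanent, although the dose table says so when it means it. A drug stopped early and not restarted could fairly be read as window treatment that had to be discontinued. The calendar footnotes even use the word for the routine last dose before surgery. The text is ambiguous; it does not exclude these patients. The ambiguity is the defect.
- **That the 21-day route is the only one.** Section 3.4 ends treatment for excessive toxicity or on the investigator's judgment. Sections 5.3 and 5.6 lead directly to permanent discontinuation for some events, such as Grade 3 creatinine, confirmed pneumonitis and, unless otherwise specified, Grade 4 events. The captured share may therefore be high.
- **That late surgery goes unmonitored.** Section 10.3.2 counts it without requiring discontinuation and at a lower boundary. What remains is narrower: patients 15 to 20 are outside that rule, and because it speaks of surgery occurring late, a cancelled operation is not clearly covered.
- **That leaving the study means loss from follow-up.** Sections 3.5, 8.3 and 10.2.2 keep such patients in follow-up. The phrase is still an undefined extra condition that the table and footnote do not carry.
- **That the tolerability report would be too favourable.** Tolerability is described for every patient with at least one dose, not from Table 8. Adverse events leading to a hold or dose reduction are recorded at any grade (Section 8.2), and the board reviews Grade 3–5 and serious events every four weeks (Section 8.4). That review has no numeric boundary, so it does not replace the rule.

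**Conclusion.** The point stands as a defect in the definition of a safety decision rule, and it should be corrected. Section 10.3.1 gives conflicting numerators for one boundary, leaves omission without resumption unclassified, and lists a qualifying toxicity that cannot register for a patient who completed dosing. The Table 8 arithmetic is correct.

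The size is illustrative because the captured share is unknown. At the plan's own 33% bound, the chance of a hold falls from 19% to 5% or 0.6% when 75% or 50% of cases are captured. At a true 50% it falls from 73% to 32% or 5%. A reader might take the 73%-to-5% contrast as the expected loss. It is not: it assumes a true rate well above the bound and that half of the cases go uncounted. If staff already record every unresumed omission as a discontinuation, nothing is lost from that source.

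**What to change.** 1. State one counted event in the text of 10.3.1, the Table 8 header and the footnote: a patient whose BYL719 was discontinued, or omitted and not resumed before surgery, because of a qualifying toxicity.
2. Delete the condition about coming off study, and change the sentence about toxicity events to match.
3. Reconcile the fourth qualifying item with 10.3.2. Either count delay beyond 42 days in Table 8 regardless of discontinuation, or leave it to 10.3.2 and extend that rule to all enrolled patients. Say which applies, and how a cancelled operation is handled.

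The boundaries and all individual dosing rules stay as written. The diary, adverse event data and surgery date are already collected.

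The cost is an amendment to wording and possibly more referrals to the board. The wider event would be judged against a prior with a 10% mean and a 33% bound that were set for discontinuations; the amendment should acknowledge this. It would also count an omission late in the window the same as one in the first week.

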10.3.2 Delay in Surgery

Because the protocol enrolls patients who will undergo potentially curative surgery, a conservative stopping rule is in place to guard against unacceptable delays in surgery. An unacceptable delay in surgery is defined as surgery occurring more than 42 days after the start of BYL719 protocol treatment, AND is due to a toxicity that is at least possibly related to BYL719 as judged by the treating investigator. Among the first 14 patients, if the number of patients with an unacceptable delay in surgery ever exceeds 3, then enrollment will be stopped and the study will be referred to the UACC DSMC for evaluation of unacceptable delays in surgery, and recommendations for study redesign or closure.

11 Study Management

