3.4 Duration of Therapy

Treatment will occur during the pre-operative window of 10-21 days or up to 28 days for delays in planned surgery or until:

- Progressive disease at any time
- Any clinical adverse event, laboratory abnormality or intercurrent illness which, in the opinion of the Investigator, indicates that continued treatment with study therapy is not in the best interest of the subject
- Excessive toxicity
- Withdrawal of informed consent (subject's decision to withdraw for any reason)
- Pregnancy
 - All women of child-bearing potential should be instructed to contact the Investigator immediately if they suspect they might be pregnant (e.g., missed or late menstrual period) at any time during study participation.
 - The Investigator must immediately notify Novartis in the event of a confirmed pregnancy in a patient participating in the study.
- Study Closure or termination
- Subject noncompliance with study procedures

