6.3 Surgery and Post-treatment Tumor Tissue Collection

6.3.1 Days 11-22 (window of +7 days up to day 29, inclusive of day of surgery)

- Oncologic head and neck cancer surgery
 - After 10-21 days of neoadjuvant treatment (+ 7 days if required for logistical and scheduling purposes), the patient will undergo the planned oncologic head and neck cancer surgery. The nature of complete resection of the primary head and neck

tumor, type of reconstruction, and levels of nodes to be dissected will be determined by the treating surgeon.

- Prior to surgery, standard of care dental evaluation is recommended, to allow for any necessary dental extractions to be planned in conjunction with surgery. Consultations with a Nutritionist and Speech and Language Pathologist are strongly recommended prior to surgery and as ongoing support post-operatively. Placement of a nasogastric (eg. Dobhoff) or gastrostomy feeding tube is at the discretion of the subject and the study physicians.
- Intraoperative tumor tissue for biomarkers (post-treatment tumor tissue collection)
 - Part of the tumor and/or lymph node specimen will be sent to the research laboratory for mandatory biomarker analyses.
 - If surgery is unexpectedly cancelled and the primary tumor or lymph node is accessible for in-office biopsy in the judgment of the surgeon-investigator, a tumor biopsy may be substituted for the intraoperative specimen.

Tissue collection procedures are described in Section 9.0.

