6.4 End-of-Treatment/Follow-up/Final Study Visit Procedures

6.4.1 4 week (+/- 2 weeks) follow-up visit

- History and physical examination
- Blood tests as clinically indicated (CBC, chemistries, liver function tests in accordance with investigator judgment)
- If pill count and medication diary did not occur previously, it will be done at the 4-week follow-up visit
- Adverse event follow up:
 - Events considered related to the study drug will be followed until return to baseline or stabilization.
 - During the post-treatment follow-up, only AEs considered related to the study drug need to be documented.
 - If a subject's surgery is cancelled but they received study drug, they will be assessed for adverse events at the 4 weeks (+/- 2 week) follow-up visit.

6.4.2 12 week (+/- 4 weeks) Final Study Visit

- History and physical examination
- Blood tests as clinically indicated (CBC, chemistries, liver function tests in accordance with investigator judgment)

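### The surgery-delay stopping rule in 10.3.2 counts only late operations, so surgery cancelled for drug toxicity is not an event under that rule

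*Combined protocol and SAP*

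**What the plan says.** Section 10.3.2 gives the rule's purpose: "a conservative stopping rule is in place to guard against unacceptable delays in surgery". The event has two parts that must both hold. The first is timing: "An unacceptable delay in surgery is defined as surgery occurring more than 42 days after the start of BYL719 protocol treatment". The second is cause: "AND is due to a toxicity that is at least possibly related to BYL719 as judged by the treating investigator". The trigger follows: "Among the first 14 patients, if the number of patients with an unacceptable delay in surgery ever exceeds 3", which means a fourth event. Enrolment then stops and the study is referred for review.

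The protocol expects that some operations will not take place. Section 6.3.1 provides for a substitute specimen: "If surgery is unexpectedly cancelled and the primary tumor or lymph node is accessible for in-office biopsy". Section 6.4.1 covers safety follow-up when a patient's "surgery is cancelled but they received study drug, they will be assessed for adverse events at the 4 weeks" visit. Neither section says how such a patient is classified under 10.3.2.

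The neighbouring toxicity rule in 10.3.1 counts patients who stop BYL719 and leave the study for a qualifying toxicity. One of its four qualifying definitions is "Any grade toxicity that results in a significant delay of surgery, defined as more than 42 days from the start of BYL719 protocol treatment". Table 8 sets its boundary at 8 discontinuations in 14 patients.

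**The concern.** The event is tied to an operation that takes place. A toxicity that pushes surgery just past the limit is an event. A toxicity that causes the surgery to be cancelled is not, although it is the worse result for a patient enrolled with potentially curative surgery planned.

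Timing is affected too. The rule acts as soon as the count passes 3, but the wording dates each event by the eventual operation. A patient still unoperated on day 60 because of toxicity has not yet met the definition, so enrolment can continue while the outcome the rule guards against has already happened.

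The monthly DSMB review in 9.4 includes the study's status against its stopping rules. For 10.3.2 that status could be reported as not met while planned operations have been lost to toxicity.

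**Working it through.** **Wording.** Three patients, each with a toxicity judged at least possibly drug-related, applied to 10.3.2 as written:

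| Patient | Timing part met? | Counted? |
|---|---|---|
| Operated 43 days after the start | Yes | Yes |
| Unoperated on day 60, surgery still planned | Not yet | Only when operated |
| Surgery cancelled | Never | Never |

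**The plan's own figures.** The documents state no operating characteristic for the delay rule, so there is none to reproduce. Table 8 for the toxicity rule was recomputed with its Beta(1, 9) prior. With 8 discontinuations in 14 the posterior is Beta(1+8, 9+6) = Beta(9, 15), the probability above 0.33 is .664, and the binomial tail at 0.33 is .054. Both match. The other five rows also match, and each boundary is the smallest count whose posterior probability exceeds 50%. So 8 of 14 is the correct comparison with 4 of 14.

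**Effect of the definition.** Inputs from 10.3.2 are n = 14 and a trigger at 4 events. Two quantities are not in the documents and are assumed over a range:
- q: the proportion of patients not operated within 42 days because of drug toxicity;
- c: the share of those whose surgery is cancelled rather than late.

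If cancellations count, the event rate is p = q. As written, it is p = q(1 − c). Since a count cannot fall, ever exceeding 3 among the 14 is the same as a final count of 4 or more:

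P(X ≥ 4) = 1 − Σ(k = 0 to 3) C(14, k) pᵏ (1 − p)¹⁴⁻ᵏ

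Worked case, q = 0.30:
- Cancellations counted, p = 0.30: 1 − (0.0068 + 0.0407 + 0.1134 + 0.1943) = 0.645.
- As written with c = 0.50, p = 0.30 × 0.50 = 0.15: 1 − (0.1028 + 0.2539 + 0.2912 + 0.2056) = 0.147.

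Full range:

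| q | Cancellations counted | As written, c = 0.25 | As written, c = 0.50 |
|---|---|---|---|
| 0.10 | 0.044 | 0.017 | 0.004 |
| 0.20 | 0.302 | 0.147 | 0.044 |
| 0.30 | 0.645 | 0.390 | 0.147 |
| 0.40 | 0.876 | 0.645 | 0.302 |

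If every failure were a cancellation (c = 1), p = 0 and the rule could not trigger at any q. These are chances of reaching the trigger by the end of the 14 patients. They do not include the further lag from waiting for a late operation before counting it.

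**The case against.** The strongest reply is that a toxicity serious enough to cancel surgery will often be counted elsewhere. Section 10.3.1 covers grade 3 or higher non-hematologic toxicity (with an exception for some electrolyte abnormalities), persistent intolerable toxicity of any grade, and grade 3 or higher thrombocytopenia or neutropenia. Its delay definition does not require that an operation has taken place, so an unoperated patient past 42 days fits its wording. A reader might therefore infer too much in saying that cancelled patients count nowhere, or that 10.3.1 has the same defect.

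That much stands, but the overlap is partial. Section 10.3.1 also requires the patient to discontinue BYL719 and come off study. Dosing lasts at most 28 days, so a patient who finishes dosing and then loses surgery to toxicity has not clearly discontinued. Monitoring begins after the sixth enrolment, and the boundary at 14 patients is twice as high.

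Three other stronger readings are tempting, and the documents do not support them:
- *That 10.3.2 is the only protection.* The DSMB reviews grade 3–5 and serious events and meets every four weeks (8.4), its chair receives each SAE within 24 hours (8.5), it reviews safety and stopping-rule status monthly (9.4), and the study can be suspended for unacceptable risk (11.7). These are real safeguards, but they rest on judgement and do not replace a pre-specified count.
- *That nothing is recorded when surgery is cancelled.* The 4-week visit includes history and physical examination (6.4.1), the reason and date of early withdrawal are documented (3.5.1), and all patients are followed for safety (10.2.2).
- *That loss of resectability through progression should be an event.* Section 3.4 lists "Progressive disease at any time" as a reason to end treatment; it does not say that surgery is then cancelled. The rule concerns drug-attributable delay, and a single-arm trial cannot separate progression on drug from natural history. Leaving progression out is defensible.

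**Conclusion.** The concern holds as a gap in one event definition. As written, 10.3.2 does not count surgery cancelled for drug toxicity and counts an overdue patient only after the late operation, although the protocol foresees cancellation. It is not an arithmetic error.

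The size depends on two rates the documents do not give. Over the assumed range, if a quarter of toxicity-related failures are cancellations, the chance of triggering falls by 0.027 at a 10% failure rate (0.044 to 0.017) and by 0.255 at 30% (0.645 to 0.390). If half are, the falls are 0.040 (0.044 to 0.004) and 0.498 (0.645 to 0.147). The loss is therefore small in absolute terms when such failures are rare and large when they are common, which is when the rule is needed. The calculation treats patients as independent with a common rate. The wording point needs no assumption about rates.

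**What to change.** In 10.3.2, define the event as planned surgery not performed within 42 days after the start of BYL719, whether delayed or cancelled, because of a toxicity that the treating investigator judges at least possibly drug-related. Count it on the 43rd day after the start, without waiting for an operation. Say explicitly that this means days elapsed, because Table 6.1 calls the first dosing day Day 1. Keep the 42-day limit and the more-than-3-of-14 threshold unchanged. Harmonise the fourth definition in 10.3.1 so that it names cancellation as well as delay.

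The cost is a few sentences and no change to any patient's treatment. The downside is that enrolment may pause slightly more often. At a 10% true rate, for example, the chance of a pause would be 0.044, instead of 0.017 if a quarter of the failures are cancellations or 0.004 if half are.

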3.2 Number of Subjects

20 patients will be accrued to achieve the target of 14 evaluable patients.

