10.2 Determination of Sample Size and Accrual Rate

10.2.1 Sample Size and Power Estimate

The primary objective of the study is to identify baseline and/or pharmacodynamic biomarkers that might have predictive utility to determine the clinical response to BYL719. The overall sample size is 14 evaluable patients. Accrual will continue until 14 evaluable patients have enrolled. If patient had baseline tissue samples obtained, has taken at least 10 doses of drug, and has undergone response assessment that is of sufficient quality to assess the primary clinical and biomarker endpoints, they are evaluable. Based upon prior window trials, up to 20 patients will be enrolled to meet these criteria. The sample size is based upon the following considerations: half of enrolled patients will demonstrate genomic PI3K pathway activation, defined as PIK3CA mutation or amplification, or PTEN deletion. We expect those with genetically activated PI3K to demonstrate a median Δ Tumor size of (-)20%, whereas those with no genomic PI3K activation to demonstrate a median increase of (+)5%. Alpha is set to 0.03 and beta is set to 0.20.

As a biomarker study, the statistical design is to accrue a sufficient number of patients and provide 80% power to test one or any of 5 key hypotheses with individual alphas of 0.03: 1) relationship between Δ Tumor size and baseline genomic *PIK3CA* activation; 2) relationship between Δ Tumor size and change in expression of HPV mRNA (qPCR); 3) relationship between Δ Tumor size and change in expression of E6, E7 oncoprotein (immunoblotting); 4) relationship between Δ Tumor size and change in expression of phospho-HER3 (immunoblotting and RPPA); 5) relationship between Δ Tumor size and change in expression of HER3/PI3K dimers (Monogram). 14 patients with complete biomarker data are needed to achieve 80% power for the 5 primary hypothesis and limit overall family wise error rate (FWER) to 15%. Based upon prior window trials, accounting for treatment compliance and quality paired tumor specimens, this will require enrollment of 20 patients.

As an example, to justify the sample size for the first key hypothesis (relationship between Δ Tumor size and baseline genomic *PIK3CA* activation), the standard deviation of Δ Tumor size

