10.2.2 Replacement Policy

Because this is an open label study with limited number of patients, 14 accrued eligible patients with clinical tumor assessments and biomarkers measurements at baseline and the end of study window are required for the study. Additional patients will be enrolled to replace patients without clinical tumor assessments and completed biomarker measurements for both timepoints and at least one of the five biomarkers of interest. However, all patients will be followed and included for safety assessments.

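### The dedicated surgery-delay rule covers only the first 14 patients although up to 20 are exposed, and delays alone in patients 15-20 cannot trip the broader toxicity rule either.

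*Combined protocol and SAP*

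**What the plan says.** Section 10.3.2 (Delay in Surgery) gives the event: "An unacceptable delay in surgery is defined as surgery occurring more than 42 days after the start of BYL719 protocol treatment", and it must also stem from a toxicity at least possibly related to BYL719. The trigger is "Among the first 14 patients, if the number of patients with an unacceptable delay in surgery ever exceeds 3", and the consequence is "then enrollment will be stopped and the study will be referred to the UACC DSMC".

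The planned exposure is larger. Section 3.2 says "20 patients will be accrued to achieve the target of 14 evaluable patients", and section 10.2.1 says "up to 20 patients will be enrolled to meet these criteria". Section 10.2.2 replaces patients who lack assessments but adds that "all patients will be followed and included for safety assessments".

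Section 10.3.1 (Toxicity) runs beside this rule. Its list of qualifying toxicities includes "Any grade toxicity that results in a significant delay of surgery, defined as more than 42 days from the start of BYL719 protocol treatment". What it counts, from the sixth patient on, is given as: "continuously monitor the number of patients who discontinue BYL719 and come off study for BYL719-attributable toxicity". Table 8 carries its boundaries to 20 subjects, and a trigger puts the study on hold and refers it to the DSMB.

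**The concern.** Fourteen is the evaluable target, not the number of people exposed. The stated reason for the delay rule is that patients are awaiting potentially curative surgery, and that applies equally to the 15th through the 20th. If the 14 are counted by order of enrolment or treatment, 6 of 20 patients (30%) fall outside the only dedicated delay limit.

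The toxicity rule runs to 20 and names delay, so it might be expected to cover the rest. Two features prevent that. It counts discontinuations, and its boundaries are set against a 33% rate with a prior centred on 10%, so they are high. At stake is whether a cluster of toxicity-related delays late in accrual would force a pause, or would depend on someone choosing to act.

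**Working it through.** **Inputs.** Delay rule: 14 patients, trips at 4 or more (10.3.2). Maximum enrolment: 20 (3.2, 10.2.1). Toxicity rule: Beta(1, 9) prior, trips when the posterior probability of a rate above 33% exceeds 50% (10.3.1). True delay rate: not given in the documents; 10%, 20% and 30% are assumed below.

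**Step 1: reproduce Table 8.** With r events in n patients the posterior is Beta(1 + r, 9 + n − r). The last column of Table 8 is the binomial tail P(X ≥ r) at 0.33.

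| n | r | Posterior, stated | Recomputed | Binomial, stated | Recomputed |
|---|---|---|---|---|---|
| 6 | 5 | .629 | .6291 | .017 | .0170 |
| 8 | 6 | .685 | .6847 | .019 | .0187 |
| 11 | 7 | .673 | .6732 | .037 | .0366 |
| 14 | 8 | .664 | .6641 | .054 | .0545 |
| 17 | 9 | .657 | .6565 | .071 | .0712 |
| 20 | 10 | .650 | .6502 | .087 | .0866 |

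The table reproduces, so the same formula can fill in the sizes it omits.

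**Step 2: can late delays alone trip the toxicity rule?** Suppose the delay rule has not tripped, so at most 3 of the first 14 were delayed. Let every later patient be delayed and, in favour of the plan, let every delay count as a discontinuation.

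| n | Smallest count that trips 10.3.1 | Largest possible number of delays |
|---|---|---|
| 14 | 8 | 3 |
| 15 | 8 | 4 |
| 16 | 8 | 5 |
| 17 | 9 | 6 |
| 18 | 9 | 7 |
| 19 | 9 | 8 |
| 20 | 10 | 9 |

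The delay count stays below the boundary at every size. At 9 of 20 (45%) the posterior is 0.498, just short of 50%.

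**Step 3: can they trip it together with other events?** Yes. Seven other qualifying discontinuations in the first 14 do not trip the rule (posterior 0.494). A qualifying delay in patient 15, if that patient discontinued and came off study, makes 8 of 15 (posterior 0.608) and does.

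**Step 4: trigger probabilities of the delay rule.** A running count that ever exceeds 3 within 14 patients is the same event as a final count of 4 or more, so the probability as written is P(X₁₄ ≥ 4). With an added cumulative limit of more than L for patients 15-20 it is

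P(X₁₄ ≥ 4) + Σ(k = 0 to 3) P(X₁₄ = k) · P(X₆ ≥ L + 1 − k).

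For example, at 20% and L = 5: 0.3018 + (0.0440 × 0.0001 + 0.1539 × 0.0016 + 0.2501 × 0.0170 + 0.2501 × 0.0989) = 0.3018 + 0.0292 = 0.331.

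| Assumed true delay rate | As written | Add more than 5 of 20 | Add more than 4 of 20 | More than 3 throughout 20 |
|---|---|---|---|---|
| 10% | 4.4% | 4.6% | 6.2% | 13.3% |
| 20% | 30.2% | 33.1% | 41.5% | 58.9% |
| 30% | 64.5% | 70.3% | 78.9% | 89.3% |

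The limits differ in strictness: 4 of 14 is 29%, 6 of 20 is 30%, 5 of 20 is 25% and 4 of 20 is 20%. The column for more than 5 of 20 is therefore the nearest to extending coverage alone.

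**The case against.** The strongest reply is that the plan does not leave late delays unwatched. Section 10.3.1 names the same 42-day event, is monitored continuously, runs to 20 subjects and puts the study on hold. The DSMB reviews safety and stopping-rule status every month (9.4), section 10.2.2 keeps every patient in the safety assessment, and section 11.7 allows suspension for unacceptable risk. All of this stands. A reader might infer from the 14-patient limit that late delays could never halt accrual, or that 10.3.2 is the sole protection of timely surgery. The documents support neither inference. But these routes need other qualifying toxicities or a discretionary judgement, and the monthly check against stopping rules has no delay limit to check once the 14 have been counted.

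Second, the 14 may mean evaluable patients. Section 10.2.1 continues accrual until 14 evaluable patients are in, so on that reading the rule could run to the end. This is possible, and it is why the denominator has to be named. It also has a cost. Evaluability requires at least 10 doses and a response assessment, so a patient whose toxicity stopped treatment early might not be counted at all.

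Third, it is arguable that a delay after completed dosing does count in 10.3.1. Dosing ends by day 28, so anyone delayed past day 42 is already off drug, and listing delay as a qualifying toxicity suggests that at least some such patients were meant. The text is unclear, and step 2 does not depend on the answer.

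Fourth, the size is easily overstated. Nine delays in 20 needs 3 in the first 14 and then all of the last six. At an assumed 20% rate its probability is 0.2501 × 0.2⁶, or about 0.00002. It shows where the boundaries lie and does not forecast what will happen.

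**Conclusion.** The point holds in a limited form. The dedicated rule is written for 14 patients of undefined type, up to 20 are exposed, and delays alone in patients 15-20 cannot trip either numerical rule. That result follows from the stated prior and criterion and needs no assumed delay rate. It does assume that the 14 are counted by order of enrolment or treatment.

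The gain from closing the gap does depend on assumed rates. With a near-proportional limit it is modest: about 0.2, 3 and 6 percentage points at 10%, 20% and 30%. A reader might take the rise from 30% to 59% at a 20% rate as the effect of covering six more patients. Most of it comes from holding the limit at more than 3 over a larger denominator, which is a stricter rule. The change is still worth making, because the gap concerns patients awaiting potentially curative surgery and a sentence or two closes it.

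**What to change.** In 10.3.2, state that the rule applies to all treated patients (up to 20). Keep more than 3 for the first 14 treated, and have the protocol team set and print a cumulative limit for patients 15-20, with its trigger probabilities at several assumed delay rates. The limits tabulated above are illustrations; the choice belongs to the team. In addition, reconcile 10.3.1 and 10.3.2 on whether a delay that follows completed dosing counts toward the toxicity rule.

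No new data are needed. The cost is a somewhat higher chance of an unnecessary referral. At an assumed 10% delay rate this is about 0.2 points (more than 5 of 20) to 2 points (more than 4 of 20) with a staged limit, and about 9 points (4.4% to 13.3%) if more than 3 is kept throughout.
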